9.9.6. Ophthalmoscopy and Optical Coherence Tomography

A complete ophthalmoscopy and OCT assessment will be performed according to the Schedule of Assessments (Appendix 1, Table 6). OCT occurring at the ET visit that are within 4 weeks of the last assessment will only be required if clinically indicated. The 2-Week Follow-Up visit assessment is only required if clinically indicated. A standard visual acuity chart should be used for the visual acuity assessment. The OCT machine used should preferably not be changed during the study to allow for comparison of central foveal thickness measurements within each subject across timepoints.

Screening Visit:

At the screening ophthalmology visit, the eye examination will include:

- Ophthalmologic history
- Best corrected visual acuity measurement (using Snellen chart internationally [if available])
- Ophthalmoscopy (may include contact lens biomicroscopy to examine the macula and optic disc). A dilated fundus exam should be performed in all subjects at the Screening Visit and as needed at subsequent visits in subjects with significant abnormalities identified on the screening exam.
- Measurement of central foveal thickness by OCT (recorded in micrometers; required for all subjects regardless of the results of visual acuity or ophthalmoscopy)
- Slit lamp examination should be performed to establish uveitis disease status (yes/no).
 Uveitis should be characterized and graded using the Standardization of Uveitis

Nomenclature criteria. Subjects with active uveitis without macular edema at Screening are eligible to enroll in the study

- If there is a suspicion of macular edema by ophthalmoscopy and increased central
 foveal thickness by OCT, then additional testing should be considered at the
 discretion of the ophthalmologist (for example, fluorescein angiogram may be
 performed). Subjects with diagnosed macular edema at Screening should be deemed a
 screening failure and should not be randomized.
- Optional procedures in case of clinically significant abnormalities on ophthalmic exam may include but are not limited to:
 - Retinal photographs
 - Intraocular pressure

Scheduled post-screening visits:

At the scheduled ophthalmology visit, the eye examination will include:

- Best corrected visual acuity measurement
- Ophthalmoscopy (may include contact lens biomicroscopy to examine the macula and optic disc)
- Measurement of central foveal thickness by OCT
- For subjects with uveitis findings on ophthalmic exam, additional testing should be considered (for example, fluorescein angiogram)

Subjects experiencing unexpected ophthalmic symptoms without a known suspected etiology or experiencing a relevant ophthalmic AE may need to have repeated ophthalmoscopy and OCT testing performed.

9.9.7. Tuberculosis Screening and Chest X-Ray

All subjects will complete TB screening to determine eligibility. A TB screening questionnaire will be completed during the Screening Period by the Principal Investigator or delegated site staff for each subject and applicable information will be entered into the eCRF. For subjects residing in countries with a high burden of TB or multi-drug resistant (MDR) TB as identified by World Health Organization (WHO), the TB screening questionnaire will be completed at every study visit (Appendix 2). For subjects who are receiving TB prophylaxis treatment, the TB questionnaire will be completed at every study visit (until TB prophylaxis treatment course is completed).

9.9.8. Clinical Laboratory Tests

Refer to Table 5 for the list of clinical laboratory tests to be performed and the Schedule of Assessments (Appendix 1, Table 6) for timing and frequency for each test. Details regarding clinical laboratory sample collection, preparation, and shipment are provided in the Laboratory Manual by the central laboratory.

Clinical safety laboratory tests should be completed pre-dose. The Investigator must review the laboratory report, document this review, and record any clinically relevant changes occurring

during the study in the adverse event section of the eCRF. Results of the total WBC and ALC will be reviewed and monitored as described in Section 9.8.5. The laboratory reports must be filed with the source documents. Clinically significant abnormal laboratory findings are those that are not associated with the underlying disease, unless judged by the Investigator to be more severe than expected for the subject's condition.

All laboratory tests with values considered clinically significantly abnormal during participation in the study or within 30 days after the last administration of study treatment should be repeated until the values return to normal or baseline or are no longer considered clinically significant by the Investigator or Medical Monitor.

- If such values do not return to normal/baseline within a period of time judged reasonable by the Investigator, the etiology should be identified, and the Sponsor should be notified.
- All protocol-required laboratory assessments, as defined in the Schedule of Assessments (Appendix 1, Table 6), must be conducted in accordance with the Laboratory Manual.
- If laboratory values from non-protocol-specified laboratory assessments performed at the institution's local laboratory require a change in subject management or are considered clinically significant by the Investigator (eg, adverse event, SAE, or dose modification), then the results must be recorded in the eCRF.

For guidance on monitoring subjects with notable lymphopenia, refer to Section 9.8.5.

Table 5: Clinical Laboratory Tests

SCREENING ONLY

Virology

HIV, HBsAg, HCV (RIBA)

Stool Sample

Bacterial culture, ova and parasites, C. difficile

Drugs of Abuse

Amphetamine, barbiturates, benzodiazepines, cocaine, methadone,

methamphetamine, methylenedioxymethamphetamine, opiate, oxycodone,

phencyclidine

Others

Hemoglobin A1C, QuantiFERON

PREGNANCY TESTING

Serum pregnancy test β-hCG - Screening

Urine β-hCG (only for women of childbearing potential)

CLINICAL CHEMISTRY, HEMATOLOGY, AND COAGULATION

Hematology Serum Chemistry

HematocritAlbuminPotassiumHemoglobinAlkaline phosphataseSodium

Mean corpuscular hemoglobin Alanine aminotransferase Thyroid-stimulating hormone

Mean corpuscular hemoglobin Aspartate aminotransferase Thyroxine free concentration Total bilirubin Bicarbonate Mean corpuscular volume Triiodothyronine free Blood urea nitrogen Platelet count C-reactive protein Total cholesterol Red blood cell count Calcium Total protein White blood cell count with Chloride Triglycerides

differential^a Creatinine Uric acid

Coagulation Creatine kinase
Direct bilirubin
Prothrombin time Glucose

Activated partial thromboplastin Gamma-glutamyl transferase

ime I and the same

International normalized ratio

Phosphorus

URINALYSIS

Appearance Nitrite
Bilirubin Occult blood

Color pH Glucose Protein

Ketones Specific gravity
Microscopic examination of Urobilinogen

sediment

Table 5: Clinical Laboratory Tests (Continued)

BIOMARKERS
Lymphocytes ^{a,b}
hs-CRP ^b
Fecal calprotectinb
CCI
STOOL SAMPLE ^c
Ova and parasites, C. difficile

- Total WBC, neutrophil, lymphocyte, and CCI will be available for review prior to randomization. After randomization, the total WBC, neutrophil, lymphocyte, and CCI cell counts will be reviewed by an unblinded Medical Monitor who will provide instructions to the site investigator in the event of significant lymphopenia. Refer to Section 9.8.5 for additional details.
- b Investigators will remain blinded to the results after randomization.
- Stool sample for bacterial culture, ova, and parasite evaluation, and C. difficile assay at any point in the study when a subject becomes symptomatic, including worsening or return of disease activity.

; WBC, white blood cells

β-hCG, beta-human chorionic gonadotropin; HBsAg, hepatitis B surface antigen; HCV, hepatitis C virus; HIV, human immunodeficiency virus; hs-CRP, high-sensitivity C-reactive protein; RIBA, recombinant immunoblot assay;

9.9.8.1. Screening

9.9.8.1.1. Drugs of Abuse

A standard urine drug screen will be performed (Table 5). Subjects who test positive will be assessed for eligibility for study participation by the Investigator.

9.9.8.1.2. Pregnancy Testing

A serum pregnancy test for β -hCG will be performed on women of childbearing potential to determine eligibility. Post-screening urine pregnancy tests (β -hCG) should be performed as indicated in the Schedule of Assessments (Appendix 1, Table 6). A monthly home pregnancy test in non-visit months should be performed and any positive result immediately reported to the study site. If the urine pregnancy test is performed at subject's home instead of onsite, pregnancy test result should be documented in their eDiary. Urine pregnancy test kits will be supplied to subjects as needed.

If at any point there is a case of a positive urine β -hCG test, the subject will have study treatment interrupted and a serum sample submitted to the central laboratory for β -hCG testing. If the serum test confirms positive, the subject will be withdrawn from the study treatment and all the necessary follow-up assessments will be conducted as per Section 9.9.10. If the serum test is negative, the subject may resume study treatment.

Negative pregnancy test results must be documented for all women of childbearing potential prior to dosing at applicable study visits. Women who are surgically sterile or who are postmenopausal are not considered to be of childbearing potential. Postmenopausal is defined as 12 consecutive months with no menses without an alternative medical cause.

9.9.8.1.3. Virology

Screening HIV antibody, hepatitis B (ie, HBsAg), and HCV (recombinant immunoblot assay, if positive HCV RNA should be used to confirm infection).

9.9.8.2. Clinical Chemistry, Hematology, Coagulation, and Urinalysis

Clinical chemistry, hematology, coagulation, and urinalysis parameters that will be assessed during the study are identified in Table 5.

Subjects will be in a seated or supine position during blood collection. All laboratory samples should be collected prior to the administration of study treatment at applicable visits (refer to Section 9.7 for timing of blood draws for PK).

9.9.9. Adverse Events

9.9.9.1. Definitions

9.9.9.1.1. Adverse Event

An adverse event is any untoward medical occurrence in a subject or clinical investigational subject administered a medicinal product and which does not necessarily have a causal relationship with this treatment. An adverse event can therefore be any unfavorable and unintended sign, symptom, or disease temporally associated with the use of a medicinal product, whether or not considered related to the medicinal product.

Adverse events can be any of the following:

- Unfavorable changes in general condition
- Subjective or objective signs/symptoms
- Concomitant disease or accidents
- Clinically relevant adverse changes in laboratory parameters over the course of the study
- Preexisting conditions that worsen in severity, increase in frequency, or have new signs/symptoms

9.9.9.1.2. Serious Adverse Event

An adverse event should be classified as an SAE if it meets one of the following criteria:

Fatal: Adverse event resulted in death.

Life-threatening: The adverse event placed the subject at immediate risk of death. This

classification does not apply to an adverse event that hypothetically

might cause death if it were more severe.

Hospitalization: The adverse event required or prolonged an existing inpatient

hospitalization. Hospitalizations for elective medical or surgical procedures or treatments planned before the signing of informed consent in the study or routine check-ups are not SAEs by this

definition.

Disabling/ incapacitating: The adverse event resulted in a persistent or significant incapacity or substantial disruption of the subject's ability to conduct normal life

functions.

Congenital anomaly or birth defect:

An adverse outcome in a child or fetus of a subject exposed to the molecule or study treatment regimen before conception or during

pregnancy.

Medically significant: The adverse event did not meet any of the above criteria but could

have jeopardized the subject and might have required medical or surgical intervention to prevent one of the outcomes listed above or involves suspected transmission via a medicinal product of an

infectious agent.

9.9.9.1.3. Adverse Drug Reaction

An adverse drug reaction (ADR) in the pre-approval clinical experience with a new medicinal product or its new usages, particularly as the therapeutic dose(s) may not be established, is any noxious and unintended response to a medicinal product related to any dose. The phrase "responses to a medicinal product" means that a causal relationship between a medicinal product and an adverse event is at least a reasonable possibility (ie, the relationship cannot be ruled out).

9.9.9.1.4. Adverse Events of Special Interest

Based on the mechanism of action of etrasimod and prior experience with other agents acting via a similar mechanism, potential adverse events of special interest may be identified. In addition to appropriate reporting of these events as an adverse event or SAE, supplementary detailed information may be collected.

If there are any signs of progressive multifocal leukoencephalopathy (PML)-related symptoms, the Investigator should withhold study treatment and perform appropriate diagnostic evaluation per local standard of care at the first signs suggestive of PML. Typical symptoms associated with PML are diverse, progress over days to weeks, and may include progressive weakness on one side of the body or clumsiness of limbs, disturbance of vision, and changes in thinking, memory, and orientation leading to confusion and personality changes. The Investigator must notify the Medical Monitor of such an event.

Guidance for the Assessment of Potential Progressive Multifocal Leukoencephalopathy is provided in Appendix 5.

9.9.9.1.5. Severity

The severity of each adverse event will be assessed at the onset by a nurse/or physician. When recording the outcome of the adverse event the maximum severity of the adverse event experienced will also be recorded. The severity of each adverse event will be graded according to the Common Terminology Criteria for Adverse Events (CTCAE), version 5.0:

Grade 1: Mild; asymptomatic or mild symptoms; clinical or diagnostic

observations only; intervention not indicated.

Grade 2: Moderate; minimal, local or noninvasive intervention indicated;

limiting age-appropriate instrumental activities of daily living (ADL).

Grade 3: Severe or medically significant but not immediately life-threatening;

hospitalization or prolongation of hospitalization indicated; disabling, limiting self-care ADL (eg, preparing meals, shopping for groceries or

clothes, using the telephone, managing money).

Grade 4: Life-threatening consequences, urgent intervention indicated.

Grade 5: Death related to adverse event.

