3.2.2. Safety Endpoint(s)

3.2.2.1. Adverse Event

AEs will be coded using MedDRA (v27.0). The version used to code AEs will be displayed in the analyses. Treatment-emergent adverse events (TEAEs) are defined as AEs that started or worsened in severity on or after the first dose of study treatment.

Refer to Section 9.1.5 for handling of partial dates for AEs for the purpose of assigning treatment-emergent flags. In the case where it is not possible to define an AE as treatment-emergent or not, the AE will be classified as treatment-emergent.

Severity of TEAEs

Severity is classified as Grade 1: Mild, Grade 2: Moderate, Grade 3: Severe, Grade 4: Lifethreatening, Grade 5: Death related to AE, using the Common Terminology Criteria for Adverse Events, v5.0 (CTCAE v5.0).

Relationship of TEAEs to Study Treatment

Relationship is classified as "not related", "unlikely related", "probably related", or "related" by the Investigator.

TEAEs Leading to Discontinuation of Study Treatment

TEAEs leading to discontinuation of study treatment will be identified by action taken being recorded as "Drug withdrawal" on the Adverse Events electronic case report form (eCRF).

Serious and Non-Serious TEAEs

Serious adverse events (SAEs) are those events recorded as "Serious" on the Adverse Events eCRF.

TEAEs Leading to Death

TEAEs leading to Death are those events which are recorded with an outcome as "Fatal" on the Adverse Events eCRF.

TEAEs of Special Interest

Categories of Targeted Medical Events (TMEs) and a list of preferred terms associated with these TME categories were developed based on the mechanism of action of etrasimod, prior experience with other agents acting via a similar mechanism, and disease-specific clinical judgment. The proposed candidate terms will be reviewed along with other supportive data (eg, vital signs, lab) to identify which events reflect AESI.

Categories and subcategories of TEAEs of special interest are the following:

- Cardiovascular Events
 - Bradycardia
 - AV conduction delay
 - Hypertension
- Macular Edema
- Pulmonary Disorders
 - Airflow obstruction (forced expiratory volume in 1 second [FEV1], forced vital

- capacity [FVC])
- Decrease gas exchange (diffusing capacity of the lungs for carbon monoxide
- [DLCO]
- Infections
 - Severe infections
 - Opportunistic infections (Narrow)
 - Herpes simplex and herpes zoster
- Liver Injury
 - Liver transaminases elevation
 - Bilirubin elevation

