6.3.1.5. Overall Summary of Adverse Events

In addition to the summaries above, an overview of TEAEs will be summarized by number and frequency of participants and by number of AEs:

- Any TEAE
- Any related TEAE*
- Any serious TEAEs
- Any related serious TEAEs*
- TEAEs leading to death
 - Liver-related TEAEs leading to death
- TEAEs leading to study treatment discontinuation
 - Related TEAEs leading to study treatment discontinuation*
 - Liver-related TEAEs leading to study treatment discontinuation
- TEAEs leading to study treatment interruption
 - Related TEAEs leading to study treatment interruption*
- TEAEs by maximum severity
- Related TEAEs by maximum severity*
- TEAEs by relationship to study treatment

^{* &}quot;Related TEAEs" refers to TEAEs related or probably related to study treatment or are missing relationship.

Comparative analyses will be performed for the following:

- TEAEs leading to Deaths
- Severe TEAEs (CTCAE grade ≥ 3)
- Serious TEAEs
- TEAEs leading to study treatment discontinuation.
- TEAEs of special interest
- Treatment-emergent Serious infections
- Treatment-emergent Opportunistic infections (Narrow)
- Treatment-emergent Malignancies

Risk differences between etrasimod and placebo along with 95% CIs using the Wilson's score method will be presented. Differences between "Exposure-Adjusted Incidence Rates" (EAIR) comparing treatment to placebo along with 95% CIs based on large-sample approximation assuming Poisson standard errors for the estimated incidence rates as described in Liu et al. will be presented as well.

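### The protocol's Grade 3 self-care examples are household tasks that on ordinary meaning belong to Grade 2, so the line that defines a severe TEAE is ambiguous

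*Protocol*

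**What the plan says.** Protocol 9.9.9.1.5 names the grading standard: "The severity of each adverse event will be graded according to the Common Terminology Criteria for Adverse Events (CTCAE), version 5.0". It then prints a short description of each grade. For Grade 2 the functional criterion is "limiting age-appropriate instrumental activities of daily living (ADL", with no examples. For Grade 3 it is "limiting self-care ADL (eg, preparing meals, shopping for groceries or", continuing "clothes, using the telephone, managing money".

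SAP 3.2.2.1 adopts the same scale: "Severity is classified as Grade 1: Mild, Grade 2: Moderate, Grade 3: Severe". Three outputs depend on the boundary between Grades 2 and 3:

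- SAP 6.3.1.1 tabulates all TEAEs, and related TEAEs, by maximum severity.
- The overview in SAP 6.3.1.5 repeats those two severity summaries.
- The list of comparative analyses in SAP 6.3.1.5 includes "Severe TEAEs (CTCAE grade ≥ 3", for which "Risk differences between etrasimod and placebo along with 95% CIs using the Wilson's score method will be presented", together with differences in exposure-adjusted incidence rates.

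The SAP version history shows that severe TEAEs were added to the comparative list in version 3.0. Incidence and severity of adverse events is a named safety endpoint in both documents (Protocol 10.11.1, SAP 2.2.2).

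**The concern.** The scale uses two kinds of activity to tell a moderate event from a severe one. The only examples given sit under self-care, yet cooking, shopping, telephoning and managing money are tasks of running a household and living independently. Self-care in the usual sense means looking after one's own body, such as washing, dressing or feeding oneself. None of the printed examples is of that kind.

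A grader faced with an event that stops a participant shopping or cooking, and does nothing more, can reach Grade 2 from the Grade 2 criterion and Grade 3 from the Grade 3 examples. Protocol 9.9.9.1.5 assigns the severity assessment to a nurse or physician, and the study is multicenter across several regions, so different sites may resolve the conflict differently. Where the printed examples are followed, moderate events can enter the severe categories of the maximum-severity tables and the between-arm comparison of severe TEAEs.

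**Working it through.** The documents give no rate of Grade 2 or Grade 3 events, so there is no plan figure to reproduce. The check is a reading of the text, followed by arithmetic on assumed values that shows only the direction and form of the effect.

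**Step 1. The two criteria side by side (Protocol 9.9.9.1.5).**

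| Grade | Functional criterion | Examples printed | Kind of activity, on ordinary meaning |
|---|---|---|---|
| 2 | instrumental ADL | none | – |
| 3 | self-care ADL | meals, groceries or clothes shopping, telephone, money | instrumental |

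The Grade 3 examples match the Grade 2 criterion. The parenthesis follows directly on the self-care wording inside the Grade 3 entry, and the Grade 2 entry is already closed, so this does not look like a text-extraction fault.

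**Step 2. Is it corrected elsewhere?** No. SAP 3.2.2.1 lists grade names only. Neither document restates the ADL criteria or provides for central review of grades.

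**Step 3. Form of the effect.** Let s be the true proportion with a TEAE of Grade 3 or higher, g the proportion whose true maximum is Grade 2, and m the share of those graded 3 because of the examples. Then:

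- observed severe rate = s + m × g
- observed risk difference = true risk difference + m × (g on etrasimod − g on placebo), if m is the same in both arms.

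Treatment is blinded (Protocol 6.5), so a common m is the reasonable default. Both severe rates rise. The risk difference moves only if Grade 2 incidence differs between arms.

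**Step 4. Arithmetic on assumed values (not estimates).**

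- With g of 20% to 40% and m of 5% to 25%, an arm's severe rate rises by 0.20 × 0.05 = 1 point to 0.40 × 0.25 = 10 points. If g differs by 10 points between arms, the risk difference shifts by 0.10 × 0.05 = 0.5 to 0.10 × 0.25 = 2.5 points.
- Alternatively, take the TEAE rates that Protocol 3.2 reports for the earlier Phase 2 study (56.0% on 2 mg, 50.0% on placebo) and assume that 5% to 15% of participants with a TEAE are moved from 2 to 3. The rise is 0.56 × 0.05 = 2.8 to 0.56 × 0.15 = 8.4 points on etrasimod, and 0.50 × 0.05 = 2.5 to 0.50 × 0.15 = 7.5 points on placebo. The net shift in the risk difference is 2.8 − 2.5 = 0.3 to 8.4 − 7.5 = 0.9 points.
- Interval width: at the planned 150 and 75 participants (Protocol 10.2) and a common severe rate p, the normal-approximation half-width is 1.96 × √[p(1 − p)(1/150 + 1/75)]. For p = 5% this is 6.0 points and for p = 10% it is 8.3 points. The SAP specifies Wilson's score method, so these widths are approximate.

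**The case against.** The strongest reply is that the printed examples are not the governing rule. The protocol tells graders to use CTCAE v5.0, and the SAP cites the same standard. A grader who opens the entry for the specific event may never rely on the parenthesis, and many events are not graded on ADL at all. This stands: misgrading is a risk, not a demonstrated effect. It does not remove the contradiction, because the protocol is itself the instruction that sites hold.

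The Grade 3 wording also carries the word disabling and opens with severe or medically significant. On one plausible reading a household limitation must also be disabling before it counts. That narrows the set of affected events. The text does not say whether the terms must be met jointly, so the ambiguity remains.

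The classification of these tasks as instrumental rests on ordinary meaning. Grade 2 lists no activities, and the CTCAE text is not in the documents. This also stands, and it is why the final wording should be checked against CTCAE v5.0.

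A reader might infer that a real imbalance in severe events would be diluted. The documents do not support that. The planned measure is a risk difference, and under blinded grading the assumed figures move it by +0.3 to +0.9 points, which is slightly upward and small beside half-widths of 6.0 to 8.3 points.

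**Conclusion.** The point holds as an error of wording in an operative grading rule. The examples printed for Grade 3 fit the Grade 2 criterion, so an event limiting only those tasks can be given either grade, and the boundary feeds the maximum-severity tables and the severe-TEAE comparison.

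The likely consequence is inflated severe rates in both arms and a somewhat wider interval. A biased risk difference is not shown; it would need Grade 2 incidence to differ between arms, or grading to differ by arm despite the blind. Nor do the documents show that sites have over-graded or that the severe row will consist largely of moderate events. The size cannot be estimated from the documents: the misgraded shares and severe rates above are assumptions, and the 56.0% and 50.0% come from a different study with a Week 12 primary endpoint, whereas this trial treats for up to 52 weeks.

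The reach is limited. Seriousness has its own definition (Protocol 9.9.9.1.2), so SAE counts do not depend on this text. Deaths and discontinuations are identified from other fields (SAP 3.2.2.1). No efficacy analysis and no test in the fixed sequence of SAP 5.1 is affected.

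**What to change.** In Protocol 9.9.9.1.5, move the parenthetical examples from Grade 3 to Grade 2, check the ADL wording of both grades against the cited CTCAE v5.0, and notify sites.

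The amendment dates from August 2022 and SAP version 3.0 from July 2024, so new wording may reach few events that are still to be graded. If data collection is largely complete, carry out a blinded medical review before unblinding of Grade 2 and Grade 3 events graded on ADL limitation. It should check in both directions, because a review of Grade 3 events alone could only lower grades. The adverse event fields listed in Protocol 9.9.9.2.2 cover description, seriousness, severity, relationship and outcome, but not the reason for a grade. A database query will therefore not identify these events, and source documents will be needed for some.

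The cost is a small wording change, a site communication and some medical review time. Some events may be re-graded. If the review finds nothing to change, the severe-TEAE comparison can be reported with that assurance.
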